3) Voluntarily seeking treatment for opioid dependence.

Method of Ascertainment: Clinical interview.

4) In otherwise good health based on complete medical history and physical examination.

Method of Ascertainment: Clinical interview and physical examination; vital signs, ECG, laboratory tests (hematology, blood chemistry, urinalysis) within normal ranges, including AST or ALT < 3 times normal limits.

5) Able to give written informed consent.

Method of Ascertainment: Clinical interview and mental status exam.

6) Failed outpatient induction onto XR-NTX in Protocol #6374 or Protocol #7190.

Method of Ascertainment: Chart review and clinical interview.

Create or insert table to describe the exclusion criteria and methods to ascertain them

1) Methadone maintenance treatment or regular use of illicit methadone (> 30 mg per week).

Method of Ascertainment: Clinical interview; urine toxicology

2) Maintenance on, or regular use of, buprenorphine or other long-acting opioid agonists.

Method of Ascertainment: Clinical interview; urine toxicology

3.) Pregnancy, lactation, or failure in a sexually active woman to use adequate contraceptive methods.

Method of Ascertainment: Clinical Interview, physical examination, urine pregnancy test during screening, serum pregnancy test at admission and day 6, at least one day prior to administration of injectable naltrexone.

4) Active medical illness which might make participation hazardous, such as untreated hypertension, acute hepatitis with AST or ALT > 3 times normal, AIDS, unstable diabetes.

Method of Ascertainment: Clinical Interview, physical examination, laboratory (Chem-20, CBC, urinalysis), ECG.

5) Active psychiatric disorder which might interfere with participation or make participation hazardous, including DSM-5 Schizophrenia or any psychotic disorder, severe Major Depressive Disorder, or suicide risk or 1 or more suicide attempts within the past year.

Method of Ascertainment: Clinical and MINI interview, clinical mental status examination, discussions with previous psychiatrist or treatment provider if formerly in treatment.

6) Physiologically dependent on alcohol or sedative-hypnotics with impending withdrawal. Other substance use diagnoses are not exclusionary.

Method of Ascertainment: Clinical and MINI interview; urine toxicology.

7) History of allergic or adverse reaction to buprenorphine, naltrexone, naloxone, clonidine, or clonazepam.

Method of Ascertainment: Clinical interview.

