Naltrexone induction procedure: Participants who successfully complete the taper must then complete a two-day washout (abstinence for opioids, buprenorphine). During this 48-hr period, participants will report to the STARS clinic daily for vital sign monitoring and to receive ancillary medications (clonidine, clonazepam, zolpidem, prochlorperazine) to alleviate withdrawal and discomfort as needed. After abstinence of $>/=48$ hours from the last buprenorphine dose, to allow for mu receptor availability, participants will begin the naltrexone induction, using a 4-day ascending taper of oral naltrexone (1, 3, 12, and 25 mg), followed by injection naltrexone. The administration of naltrexone will occur within a detoxification suite provided at STARS, consisting of a private room outfitted with two comfortable reclining lounge chairs for resting, adjustable lighting, and an entertainment system. Participants will be monitored by clinical staff at least every 1-2 hours with frequent vital signs checks and withdrawal assessments. A research psychiatrist or study physician will be present at all times to conduct frequent clinical assessments and provide adjuvant medications and naltrexone. Patients will be monitored on a daily basis (Monday to Friday) for up to 8 hours per day. Transportation home by car service will be provided at the end of the day for any patient deemed to have this clinical need.

As per the dosing schedule in the protocol #6374, on Day 1 of the naltrexone induction, participants are pre-treated with prochlorperazine 10 mg for nausea, followed by the first dose of naltrexone 1mg. Ascending doses of naltrexone will then be titrated upward slowly (3mg, 12mg, 25mg). Adjuvant medications will be available to patients and will include clonidine for myalgias, prochlorperazine for nausea, clonazepam to reduce anxiety and dysphoria, and trazodone or zolpidem for insomnia. Participants will be provided take-home doses of adjuvant medications in small doses and on a tapering schedule for one week post-administration of XR-NTX. Participants will be required to visit the clinic daily and remain there for at least 1 hour to permit close monitoring, with an option to stay as long as necessary to achieve relief of symptoms and medical stability prior to being discharged home.

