Pregnancy: Both the buprenorphine-clonidine-naltrexone procedure and naltrexone maintenance are considered contraindicated in pregnancy. Several small case series (Hulse et al., 2001; 2004) are reassuring in suggesting favorable pregnancy outcomes in women detoxified and maintained on naltrexone while pregnant. However, standard practice suggests methadone maintenance is the treatment of choice for opioid dependent pregnant women, and we do not consider the small size of these case series sufficient to amend that recommendation. Absence of pregnancy will be confirmed at baseline and monthly during the study with urinary HCG. During the inpatient detoxification period, a serum (quantitative) pregnancy test will be obtained on admission and repeated on the day prior to administration of depot naltrexone. For women, regular use of an adequate contraception method (diaphragm with spermicide, condom with spermicide, birth control pills) is required for inclusion in the study. Patients who become pregnant during the trial

will be removed from the trial and treated as clinically indicated.

Blood Tests: Blood drawing may cause slight discomfort at site of needle entry, resulting in a small bruise. Other risks include patients' discomfort with being asked uncomfortable questions or the psychological distress that may occur if a patient agrees to be tested for HIV.

Risks associated with receiving vouchers or cash equivalents: An incentive system is being used to compensate patients for their time and travel and to encourage compliance with study procedures. For that purpose we have adopted procedures used widely in the context of Contingency Management Therapy. We believe that using low-value incentives is essential to maximize participation in study-related procedures, including nursing and physician visits for safety monitoring, study outcomes collection, and therapy participation. Risks that participants will attempt to use study payments to purchase drugs, though still present, are rather small with current procedures.

Describe procedures for minimizing risks

The exclusion criteria of this study are designed to minimize the risks to participants.

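### No pregnancy test is firmly tied to the first oral naltrexone dose, because the serum tests are dated by an admission and a day 6 that this outpatient study does not define

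*Protocol*

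**What the plan says.** Exclusion 3 (Protocol, Inclusion/Exclusion Criteria) lists a urine test at screening and then a "serum pregnancy test at admission and day 6, at least one day prior to administration of injectable naltrexone". The Pregnancy paragraph under Risks gives a similar rule: "During the inpatient detoxification period, a serum (quantitative) pregnancy test will be obtained on admission and repeated on the day prior", where the second test is "repeated on the day prior to administration of depot naltrexone". It adds: "Absence of pregnancy will be confirmed at baseline and monthly during the study with urinary HCG".

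The naltrexone induction text (Protocol, Study Procedures) mentions no pregnancy test between the taper and oral dosing. For the washout it says "During this 48-hr period, participants will report to the STARS clinic daily for vital sign monitoring" and mentions ancillary medication. It then says that "on Day 1 of the naltrexone induction, participants are pre-treated with prochlorperazine 10 mg for nausea, followed by the first dose of naltrexone 1mg". A urine test appears later, on the day of the XR-NTX injection.

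Four other places put the serum test at screening: Clinic visits, Blood and other Biological Samples, Medical Evaluation and Monitoring, and the procedures for minimizing risks.

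On the hazard, the Pregnancy paragraph states: "Both the buprenorphine-clonidine-naltrexone procedure and naltrexone maintenance are considered contraindicated in pregnancy". A woman who becomes pregnant "will be removed from the trial and treated as clinically indicated". The SAP does not touch on this point.

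**The concern.** The Protocol treats the induction procedure as contraindicated in pregnancy, not only the depot injection. Naltrexone starts about a month after baseline, so a negative screening test cannot rule out a pregnancy that begins during the buprenorphine taper. The natural place for a fresh check is the washout, just before the 1 mg dose.

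The tests that might serve this purpose are dated by terms that do not fit the study. Detoxification here takes place in an outpatient clinic, so there is no inpatient admission, and day 6 has no stated day 1. Two staff members could follow the same text and act differently: one would draw serum as the washout begins, the other would regard the screening sample as enough. In the second case, a pregnancy begun during the taper could go unseen until oral naltrexone had been given, unless the monthly HCG happened to fall at the right time.

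**Working it through.** There is no plan figure to reproduce. The check is to lay out the schedule and place each stated test on it.

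**Inputs.** The dated buprenorphine schedule ends on Day 30. A two-day washout and four days of oral naltrexone (1, 3, 12 and 25 mg) follow, then the injection (all Protocol, Study Procedures). Taking two full washout days:

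- washout: Days 31–32
- oral naltrexone: Days 33–36
- injection: Day 36, or Day 37 if given the day after the 25 mg dose

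Monthly is taken as 28 to 31 days. The lag from screening to buprenorphine Day 1 is not given; 7 and 14 days are shown as assumptions.

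| Test | Counted from | Falls on | Relative to the first oral dose (Day 33) |
|---|---|---|---|
| Serum at admission | start of washout | Day 31 | 33 − 31 = 2 days before |
| Serum on day 6 | washout start as day 1 | Day 36 | 36 − 33 = 3 days after |
| Serum at admission | intake or screening | Day 1 or earlier | 33 − 1 = 32 days or more before |
| Serum on day 6 | buprenorphine Day 1 | Day 6 | 33 − 6 = 27 days before |
| Monthly urine | buprenorphine Day 1 | 1 + 28 = Day 29 to 1 + 31 = Day 32 | 4 to 1 days before |
| Monthly urine | screening 7 days earlier (assumed) | Days 22–25 | 11 to 8 days before |
| Monthly urine | screening 14 days earlier (assumed) | Days 15–18 | 18 to 15 days before |
| Pre-injection serum | day before injection | Day 35 or 36 | after 2 to 4 of the 4 oral doses |
| Injection-day urine | injection | Day 36 or 37 | after oral dosing has begun |

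If the first oral dose is given exactly 48 hours after the Day 30 buprenorphine dose (Day 32), each interval before the dose is one day shorter: 1 day; 26 or at least 31 days; and 0–3, 7–10 or 14–17 days for the monthly urine.

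Counting day 6 from the first naltrexone dose gives 33 + 5 = Day 38. That is after the injection, so it contradicts exclusion 3 itself.

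**Which reading of admission?**

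- *Start of detoxification.* Exclusion 3 lists the screening urine test apart from the admission serum test. The Pregnancy paragraph places the admission test in a detoxification period. The early-discontinuation criteria list detoxification apart from the taper. Day 6 from the washout start is also the day before a Day 37 injection.
- *Intake or screening.* Recruitment Procedures uses admission for clinic intake. Four sections put the serum test at screening, and the risk-minimization text states the same quantitative serum test with screening as its time.

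The first reading fits exclusion 3 better, but no text adopts it. The monthly HCG does not settle the matter, because the Pregnancy paragraph pairs it with baseline while the risk-minimization text pairs it with screening.

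**Number affected.** Sample Demographics gives 3 + 1 + 1 = 5 women among 30 enrolled. Only those who complete the taper would reach the first oral dose.

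**The case against.** A reader might infer that women go a month without a pregnancy test before naltrexone, or that the injection is unprotected. The documents support neither. On the reading that exclusion 3 favours, a serum test comes 2 days before the first oral dose. On the other reading, a monthly HCG counted from buprenorphine Day 1 still falls 1 to 4 days before it. The older ages for that test depend on assumed screening lags, and the benefits section says that participants are eligible as soon as they leave the parent trial, so the lag may be short. The injection is preceded by a serum test and a same-day urine test. Nothing suggests that a pregnant woman was dosed.

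It can also be said that the contraindicated procedure, as described under Risks, begins with buprenorphine stabilization, so the hazard starts on Day 1, where screening covers it. The oral exposure at issue is 1 + 3 + 12 + 25 = 41 mg over four days, less than one 50 mg daily maintenance dose. Contraception is required. Interventions are complete, so no participant can now be protected.

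All of this limits the weight of the point. It does not supply an anchor for admission or day 6, and any cover from the monthly test depends on where the month is counted from. Because the procedure named as contraindicated includes naltrexone, a negative test at entry does not remove the reason to check again before naltrexone is first given.

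**Conclusion.** The point holds as a minor safety correction. The serum-test rule cannot be followed as written in an outpatient study, and no test is firmly tied to the first oral naltrexone dose. Depending on what admission means, the last serum test before that dose is 2 days old, or 27 or at least 32 days old. In the latter case only a monthly urine HCG with no fixed start fills the interval.

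The day counts assume the 30-day dated schedule and two full washout days; the 8–18 day ages for the monthly test also assume a screening lag of 7 or 14 days. At most five women are concerned. The documents do not support a claim that testing before naltrexone is absent, only that it is not clearly required. No endpoint, estimate or analysis is affected.

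**What to change.** 1. **Study Procedures, washout.** Add: *Female participants must have a negative urine pregnancy test at a washout visit, before the first 1 mg naltrexone dose. If it is positive, no naltrexone is given and the participant is removed as described under Pregnancy.*
2. **Exclusion 3.** Change the serum timing to: *during screening and at least one day prior to administration of injectable naltrexone*. This drops admission and day 6.
3. **Risks, Pregnancy.** Delete *inpatient*, change *on admission* to *during screening*, and give the pre-injection serum test as *at least one day prior*. Fixing it to the day before would need a Sunday draw for a Monday injection, since daily monitoring runs Monday to Friday.
4. **Keep** the monthly HCG and the injection-day urine test as they are. With a washout urine test in place, a serum test at the start of washout is not needed as well.

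The cost is three text edits and one urine test per woman who completes the taper. Washout visits are already daily and urine is already collected at every visit, so no visit or sample is added. If staff had read admission as the start of detoxification, the urine test takes the place of a serum draw at that point. Since interventions are complete, the change corrects the protocol on file and any later study that reuses its text.

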**Statistical Analysis:**

This is a single-arm, open-label, pilot study evaluating whether individuals with opioid use disorder who were unable to tolerate a rapid transition to XR-naltrexone would tolerate a slow four-week buprenorphine taper and XR- naltrexone induction.

Study objective was to evaluate the feasibility of the slow-transition protocol and to obtain descriptive data regarding baseline demographics and treatment outcomes in such patients.

Analytical plan include: 1) percent of participant who completed the transition, 2) time to relapse defined as daily opioid use for 5 days or study dropout, and 3) descriptive statistics on baseline characteristics comparing participants who successfully initiated XR-NTX and those who did not initiate XR-NTX. Summary statistics will include frequency, percentages, and where relevant averages.

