To date, there is no standard buprenorphine detoxification design, and data of duration of buprenorphine detoxification, and its impact on treatment outcomes, has been mixed. A review of the literature by Dunn et al. in 2011 suggests buprenorphine taper duration is associated with opioid abstinence, but not retention (Dunn et al. 2011). However, there are relatively few randomized, clinical trials of taper duration. Some trials suggest longer tapers are associated with less withdrawal, less opioid use and better retention (Amass et al. 1994; Woody et al. 2008; Sigmon et al. 2013). However, Ling et al. found a larger percentage of opioid negative urines in their shorter taper group (Ling et al. 2009). In a recent randomized, double-blind trial, Sigmon et al. compared the relative efficacy of 1-, 2-, and 4-week buprenorphine tapering regimens and subsequent naltrexone induction (Sigmon et al 2013). They found a significant effect of taper duration on abstinence, retention, and naltrexone ingestion at the end of their 12-week study (Sigmon et al 2013).

In one of our ongoing studies, Long-acting Injectable Naltrexone Induction: A Randomized Trial of Outpatient Opioid Detoxification with Naltrexone vs. Buprenorphine (PI: [name], (#6374) opioid-dependent participants are randomized to one of two outpatient detoxification strategies: (1) a standard 7-day buprenorphine induction and gradual taper from 8 mg to 0 mg vs. (2) 7-day oral naltrexone induction. Both groups receive a single administration of a long-acting injectable naltrexone (XR-NTX): at Day 8 for the naltrexone induction group and Day 15 for the buprenorphine group. Thus far, we have demonstrated successful outpatient induction onto long-acting injectable naltrexone (XR-NTX) at a rate of about 50%; the naltrexone treatment arm has achieved better rates of successful induction onto XR-NTX compared to the buprenorphine-assisted detoxification arm, but the difference has not yet reached statistical significance (53% vs. 42%).

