In another one of our ongoing studies, A Phase 3 Study to Evaluate the Safety, Tolerability, and Efficacy of Naltrexone for use in Conjunction with Buprenorphine in Adults with Opioid Use Disorder Prior to First Dose of Vivitrol (PI: [name], (#7190) opioid-dependent participants are randomized to one of three outpatient 8-day detoxification schedules: (1) oral naltrexone + buprenorphine (2) oral naltrexone+ placebo buprenorphine (3) placebo oral naltrexone + placebo buprenorphine. All three groups receive a single administration of a long-acting injectable naltrexone (XR-NTX) on Day 8.

Therefore, in the current pilot study, we would like to implement a procedure for retaining in treatment patients who fail the initial attempt at outpatient detoxification and XR-NTX induction. This procedure will

be similar to the approach of Sigmon et al. 2013, with a 4-week period of buprenorphine stabilization and taper off. Participants will then repeat the detox using a 2-day washout followed by a 4-day ascending taper of oral naltrexone (1, 3, 12, and 25 mg), with the purpose of XR-NTX induction. Including a buprenorphine maintenance arm allows for a period of stabilization and relief from withdrawal symptoms, followed by a taper, with the thought that this may be more tolerable to these individuals that have previously had a difficult time modulating and tolerating the distress of the more rapid detoxification.

Specific Aims and Hypotheses

Specific Aims and Hypotheses

SPECIFIC AIM #1: To test the efficacy of a second-line treatment for the 50% of opioid-dependent individuals who fail their first attempt at outpatient XR-NTX induction. The primary outcome is successful induction onto XR-NTX.

EXPLORATORY AIMS: We will also examine secondary outcomes retention (time to drop-out); severity of opioid withdrawal; and 2-week abstinence at 3rd and 4th weeks after XR-NTX injection.

Description of Subject Population

Sample #1

Specify subject population

Adults 18-60 years old, who meet current DSM-5 criteria for OUD of at least moderate severity

Number of completers required to accomplish study aims

14

Projected number of subjects who will be enrolled to obtain required number of completers

46

Age range of subject population

18-60

Gender, Racial and Ethnic Breakdown

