How will the study be advertised/publicized?

Advertising, recruitment, and screening is covered under the STARS Umbrella Screening protocol 6582R. We will use IRB-approved advertisements to reach our target population.

Do you have ads/recruitment material requiring review at this time?

No

Does this study involve a clinical trial?

Yes

Please provide the NCT Registration Number

NCT02294253

Concurrent Research Studies

Will subjects in this study participate in or be recruited from other studies?

Yes

Describe concurrent research involvement

DA030484-04: "Long-acting Injectable Naltrexone Induction: A Randomized Trial of Outpatient Opioid Detoxification with Naltrexone vs. Buprenorphine." (IRB# 6374). In the ongoing study funded by DA030484-04, we compare a rapid, 7-day induction method (one day of buprenorphine followed by a gradual titration of oral naltrexone and injectable naltrexone administration) to a standard 14-day procedure (involving a week-long buprenorphine taper followed by a week-long washout and injectable naltrexone

administration). To date we have enrolled 110 participants in 3 years of enrollment; recruitment has been twice as fast as predicted (based on previous inpatient studies) because of a high level of interest in the outpatient procedure.

ALK6428A-301. "A Phase 3 Study to Evaluate the Safety, Tolerability, and Efficacy of Naltrexone for use in Conjunction with Buprenorphine in Adults with Opioid Use Disorder Prior to First Dose of Vivitrol" (IRB #7190). In the ongoing study funded by Alkermes Inc., in a randomized double-blind trial, we compare three different treatment arms (1) oral naltrexone + buprenorphine, (2) oral naltrexone + placebo buprenorphine, (3) placebo oral naltrexone + placebo buprenorphine over 8 days, followed by administration of XR-NTX. To date we have enrolled 12 participants, randomized 4, and 1 participant has been successfully inducted onto XR-NTX.

Inclusion/Exclusion Criteria

Name the subject group/sub sample

Adults 18-60 years old

Create or insert table to describe the inclusion criteria and methods to ascertain them

1) Age 18-60.

Method of Ascertainment: Clinical interview

2) Meets DSM-IV criteria for current opiate dependence disorder of at least six months duration, supported by urine toxicology OR COWS score > or =6 OR Naloxone Challenge.

Method of Ascertainment: Clinical and MINI interview, urine toxicology or COWS score > or = 6, or naloxone challenge.

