Buprenorphine induction/stabilization/taper: Buprenorphine induction will be conducted at our STARS clinic and according to current clinical guidelines. Participants who have initially failed outpatient induction onto XR-NTX will receive buprenorphine/naloxone (BUP) on a weekly basis that they will take daily, according to the following schedule: 8/2 mg (Days 1-10), 6/1.5 mg (Days 11-15), 4/1 mg (Days 16-20), 3.0/0.75 mg (Days 21-25), 2.0/0.5 mg (Days 26-30). Participants will attend the clinic twice weekly and will be assessed for opioid and other substance use (urine toxicology and self-report), vital signs, opioid withdrawal symptoms, opioid cravings, and dose adjustments of buprenorphine will be made as needed by study physicians. If a dose reduction is needed, the stabilization and taper schedule will be adjusted to occur over 30 days. Participants will be stabilized on, and tapered off, buprenorphine over a 4-week period.

Reductions will occur in a graded fashion, with the stabilization dose reduced to 2 mg. This approach to buprenorphine taper is intended to resemble standard clinical practice, in which patients seeking transition off buprenorphine undergo a slow taper. A gradual taper over approximately 4 weeks has established precedent (Sigmon et al. 2013, Ling et al. 2009, Nielsen et al. 2013) as a well-tolerated taper strategy for transitioning off buprenorphine. The purpose is in part to provide a slow transition with minimal withdrawal symptoms. Participants will have at least two study visits a week during the buprenorphine taper, but may be seen more regularly at STARS if deemed clinically necessary.

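### Does the SAP's phrase about intolerance of a rapid transition call for a narrower population or a split by parent-trial arm?

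*SAP*

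**What the plan says.** The SAP's opening paragraph calls this a single-arm, open-label pilot in "individuals with opioid use disorder who were unable to tolerate a rapid transition to XR-naltrexone", who are then offered a slow four-week buprenorphine taper and a second induction. It lists three analyses: the percentage completing the transition, time to relapse, and baseline characteristics of those who did and did not start XR-NTX. None is broken down by parent protocol, parent arm or reason for the first failure.

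The protocol words the population more broadly. Inclusion criterion 6 reads "Failed outpatient induction onto XR-NTX in Protocol #6374 or Protocol #7190". Aim 1 concerns "individuals who fail their first attempt at outpatient XR-NTX induction". Study Procedures begins with "Participants who have initially failed outpatient induction onto XR-NTX". None of these restricts by arm or by reason.

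Under Concurrent Research Studies, the protocol says of #6374 that "we compare a rapid, 7-day induction method" against a "standard 14-day procedure (involving a week-long buprenorphine taper followed by a week-long washout". The Background section puts that second arm's injection at "Day 15 for the buprenorphine group".

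**The concern.** Two gaps seem to open between the label and the people enrolled.

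- **Rapid.** The protocol attaches this word to one arm of #6374 and calls the other arm standard. Failures of both arms are eligible, so some participants may never have attempted what the protocol itself calls a rapid induction.
- **Unable to tolerate.** Someone can fail an induction by refusing the injection or by not attending, which is not obviously intolerance.

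If second-attempt success depended on which regimen failed first, the pooled percentage would shift with the mix of parent arms, and the SAP does not plan to report that mix. A reader could then take a figure from a mixed group as the success rate after a failed rapid transition. At stake is whom the result describes; no error rate is involved.

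**Working it through.** **Step 1: does the phrase alter any denominator?** Eligibility is set by inclusion criterion 6, and Aim 1, the recruitment text and Study Procedures agree with it. The SAP defines no analysis set from its opening phrase and excludes no one on the basis of parent arm. All three planned summaries are the same whichever wording is used.

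**Step 2: what does rapid mean in the SAP sentence?** The protocol gives these schedules:

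| Regimen | Before the injection | Injection |
|---|---|---|
| #6374, naltrexone arm | one day of buprenorphine, then oral naltrexone | Day 8 |
| #6374, buprenorphine arm | one-week taper, one-week washout | Day 15 |
| #7190, all three arms | 8-day schedules | Day 8 |
| This study | 30 days of buprenorphine, 2-day washout, 4 days of oral naltrexone | 30 + 2 + 4 = Day 36 or later |

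The SAP sentence sets rapid directly against this study's slow taper. On that comparison every parent regimen is rapid, including the 14-day arm. The Background section of the protocol uses the comparative form too: it explains the longer stabilization by the trouble these patients had in tolerating the distress of a more rapid detoxification. That passage follows the descriptions of both parent trials and does not separate their arms. The contrast under Concurrent Research Studies is between two arms of another trial and does not define the word for this SAP.

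**Step 3: failed or unable to tolerate?** The same Background passage treats first failure as difficulty in tolerating detoxification, so the SAP is not alone in this usage. The parent trials' definitions of failure are not in the documents. This study's own dropout criteria during detoxification count continued opioid use as inability to tolerate oral naltrexone, but list injection refusal and a 7-day absence separately. Those criteria do not govern how #6374 or #7190 classified failure, so they neither prove nor remove the gap.

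**Step 4: can a size be given?** The only sourced inputs are the interim induction rates in #6374: 53% (naltrexone) and 42% (buprenorphine), a difference that the protocol says was not yet significant. Failure rates are therefore 47% and 58%. With r the naltrexone:buprenorphine allocation ratio, which is not stated:

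14-day share of #6374 failures = 0.58 / (0.58 + 0.47r)

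- r = 1: 0.58 / 1.05 = 55%
- r = 2: 0.58 / 1.52 = 38%
- r = 0.5: 0.58 / 0.815 = 71%

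These are shares of eligible #6374 failures, not of participants here. The pooled percentage differs from the rapid-only one by w × d, where w is the 14-day share of the sample and d the difference in second-attempt success. Neither is documented. Purely as an illustration, if everyone came from #6374 and d were 20 points, the gap would be 0.55 × 20 = 11 points (7.6 to 14.2 over the range of r). If d = 0, it is zero. For scale, an illustrative 15/30 has an exact 95% interval of 31% to 69%, about 19 points either side.

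**Step 5: would a split help?** A stratum of 10 with 5 successes has an exact 95% interval of 19% to 81%. That could not show whether parent arm matters.

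**The case for a change.** The best case for a change is that the SAP's objective refers back to the patients described in its first sentence, so the label governs what the study says it estimates. In a descriptive pilot, the identity of the patients is much of what the percentage conveys. When the protocol text was written, #6374 had enrolled 110 people, against 12 enrolled and 4 randomized in #7190, so a negligible 14-day share cannot be assumed. Analysis is still under way, and a reworded sentence with one descriptive table would cost little.

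Part of this stands. The phrase is literally narrower than criterion 6, and the comparative reading of rapid leaves failed and unable to tolerate as different words. But the argument does not identify a planned number that would be wrong. It needs second-attempt success to differ by parent arm, and the documents give no figure for that. The third SAP item does not list its baseline characteristics, so analysts may already tabulate parent protocol and arm there. Low cost alone does not make a table necessary when it could support no inference.

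**Conclusion.** No change to the plan is needed. The SAP's opening phrase is a loose summary of the eligible group. Criterion 6 fixes who is counted, and the pooled percentage answers Aim 1 as written. The rapid half of the mismatch largely disappears once the word is read against the slow taper in the same sentence. The other half is a difference in wording that analysts can settle by describing participants in the terms of criterion 6 when they report.

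No planned figure moves. The 38% to 71% share rests on interim rates and an assumed allocation ratio, and any distortion also needs an undocumented sample mix and an undocumented difference in success, which may be zero. This conclusion assumes that the report claims no more than Aim 1 does: success among people whose first outpatient induction failed. A claim confined to failures of the 7-day arm alone would need its own denominator, but the SAP does not plan one.
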